1. SUMMARY

Study Title	Baduanjin mind-body exercise for cancer-related fatigue in cancer participants receiving adjuvant chemotherapy: a randomised control feasibility trial
Aims/Objectives	
Primary
 
The feasibility and acceptability of remotely delivered Baduanjin mind-body exercise (the study protocol) via recruitment, retention, and adherence rates.
 
Secondary
 
A reduction in the severity of cancer-related fatigue symptoms measured by the Brief Fatigue Inventory (BFI). The improvement in health domains relating to physical function, fatigue, pain interference, depressive symptoms, anxiety, ability to participate in social roles and activities, and sleep disturbance measured by PROMIS–29 Profile v2.0 and the number and severity of adverse events (AEs).
 
Participant’s ratings of the intervention before and after using a modified Credibility and Expectancy Questionnaire.
 
Reporting participation frequency via the Baduanjin Mind-Body Exercise Logbook.

Study design	Pilot randomised wait-list controlled feasibility trial
Planned sample size	40 (n = 20 per group)
Inclusion criteria	(1) 18 years of age or older; (2) receiving adjuvant chemotherapy or completed adjuvant chemotherapy; (3) medical history of cancer diagnosis; (4) suffering from moderate Cancer Related Fatigue (CRF) as assessed by the simple fatigue scale (from the BFI); (5) have a computer / device that is Wi-Fi or hotspot connected and be able to use smart phones, email and Zoom conferencing app; (6) be aware of one’s disease diagnosis; and (7) understand the intervention process and able to communicate and provide informed consent in English.
Study procedures	Eligible participants will be identified and referred by their treating oncologist, a health care team member or self-referral from advertising. The participants will be randomly assigned in a 1:1 ratio to the Baduanjin mind-body exercise or wait-list control groups respectively. Intervention group data will be collected at baseline (week 0), at 4 weeks, 8 weeks and one-week follow-up (week 9). Waitlist control group data will be collected at recruitment (week 0) and at week 4, week 8 and week 9 (follow-up).
Analysis considerations	
Sample size calculation: For a pilot study, a sample size of n = 29 is necessary to have a 95% confidence of detecting an event which has a true probability of $\pi = 0.10$. As the participants will be randomised into two groups with a 1:1 allocation ratio, and to overcome the probable potential 15% attrition of participants during the study period, while ensuring availability of sufficient participants, a sample size of n=40 will be recruited in this study.
 
Analysis plan: Analyses of the endpoints will follow the ‘intention to treat’ and ‘per-protocol’ approaches.
 
Demographics and data will be descriptively summarised at

Study duration	baseline using sample means and proportions with corresponding 95% confidence intervals. The primary or secondary outcomes will be addressed using a mixed linear model over time. 10 weeks. This includes 1 week for baseline measures (week 0), 8 weeks of intervention (or waitlist control) (week 1-8), and 1 week follow-up (week 9).
-----------------------	---

2. BACKGROUND AND RATIONALE

Cancer-related fatigue (CRF) is a commonly reported cancer or cancer-related treatment side effect [1]. The National Comprehensive Cancer Network (NCCN) defines CRF as ‘a distressing, persistent, subjective sense of physical, emotional and/or cognitive tiredness or exhaustion related to cancer or cancer treatment’ [2]. While most severe in the first 6 months following a cancer diagnosis or treatment, CRF can persist for years [3] and remain present throughout the disease trajectory. CRF is notable for being resistant to relief by rest or sleep and the fatigue is disproportional to recent activity, affecting a person’s everyday functioning and quality of life [1, 2].

Most of the population living with a cancer diagnosis report CRF. The NCCN (2016) guidelines reported 80% of participants surveyed (n=1569) experienced CRF following chemotherapy and/or radiotherapy [2], while conservative estimates report this figure as 60-96% of the population [4]. Fatigue is perceived as the most distressing cancer or cancer treatment related symptom experienced. Unlike nausea or vomiting, which is generally manageable with anti-emetics, healthcare practitioners find fatigue challenging to manage [2, 5, 6]. Additionally, advances in treating cancer and improving survivorship rates means more people are living with a disability-related fatigue issue [2]. Consequently, CRF is a significant area of research to support and improve quality of life outcomes for people diagnosed with cancer, and especially given the persistence of CRF into the post-cancer treatment period.

Current treatment options have tended towards recommending exercise-based activities over pharmaceutical interventions. NCCN Clinical Practice Guidelines in Oncology for Cancer-Related Fatigue note the benefits of physical exercise in reducing CRF [2]. A meta-analysis of 26 qualified RCT studies additionally concluded aerobic exercise effective for managing CRF in cancer patients who had completed adjuvant therapy [7]. Cochrane reviews report aerobic exercise reduced CRF both during and after treatment, specifically in people with solid tumours [8, 9]. The benefits of exercise may alleviate both the cognitive and physiological effects of fatigue [10, 11].

Exercise and psychological treatments were reported as better than available pharmaceutical treatments in reducing CRF, both during cancer treatment and in the cancer post-treatment stages [11]. A meta-analysis of non-pharmaceutical cognitive, manual, and mind-body therapies (including tai chi and yoga) reported mild to moderate

effects on alleviating CRF [12]. It was concluded that patients can choose from among different effective types of exercise and non-pharmaceutical interventions to reduce CRF.

One such physical exercise intervention is Baduanjin mind-body exercise, which is a practice akin to Tai chi (Tai ji) originating from China. Well-known within Chinese Medicine's health care practice scope, Baduanjin mind-body exercise is the most widely used mind-body exercise in China [4]. In Australia, Baduanjin mind-body exercise is frequently prescribed to patients by Ahpra Chinese Medicine Board Australia (CMBA) registered health care practitioners to assist with health maintenance or support patients' health recovery and maintenance, and physical mobility.

Baduanjin mind-body exercise involves a set of gentle aerobic exercises involving mental focus with controlled breathing while performing a sequenced set of coordinated physical movements [4, 13, 15]. According to the American Sports Medicine Association and the American Centres for Disease Control and Prevention, Baduanjin mind-body exercise is a low-intensity exercise. The metabolic equivalent of Baduanjin mind-body exercise is < 3.0 and the maximum heart rate is 54% [14]. As a low-intensity exercise, Baduanjin mind-body exercise can build muscles, boost perceived energy levels, and improve the participant's body functioning. It can also mediate the stress response and alleviate anxiety, inducing a perceived sense of relaxation and calm, and is associated with reduction in the progression of serum-related anxiety markers [16]. Overall, Baduanjin mind-body exercise training has been shown to reduce fatigue, increase maximum oxygen uptake and muscle strength, improve sleep quality and overall quality of life, without causing significant adverse events [4, 13, 17-20].

A systematic review presented that Baduanjin mind-body exercise is beneficial for quality of life, sleep, general life balance, and physical parameters (hand grip strength, flexibility, blood pressure, and heart rate) among healthy individuals [11, 12] and participants with a variety of diseases [21-23]. Two clinical studies showed that Baduanjin mind-body exercise significantly reduced fatigue and improved perceptions of quality of life of colorectal cancer participants undergoing chemotherapy and breast cancer survivors who completed chemotherapy [4, 5].

Despite evidence showing benefits to survivability and quality of life, people living with a cancer diagnosis face additional barriers to participating and adhering to prescribed exercise interventions [24]. Barriers extend across several domains that include physical (muscle weakness, pain, fatigue), psychological (self-conscious about appearance, procrastination), environmental (weather, lack of equipment) and social (lack of company)

[24, 25]. Distinctly, Baduanjin mind-body exercise whilst providing exercise-like benefits [4], provides a low impact and low intensity intervention that combined with regulated breathing and mindfulness practices can assist patients who cannot otherwise participate in standardised exercise interventions. Baduanjin mind-body exercise may therefore be an appropriate form of exercise in lieu of other prescribed exercises for patients who have difficulty performing aerobic and/or strength training exercises.

However, further study is required to investigate the receptiveness of Baduanjin mind-body exercise for CRF in an Australian-based cancer-care context and population. Additionally, while useful for CRF, these studies were conducted through face-to-face instruction, which is not always suitable for people who find travelling difficult when fatigued, who are living in rural or remote locations or who are in isolation due to risk of acquiring a secondary infection. Consequently, the study additionally proposes a remote delivery model for the intervention.

3. STUDY AIMS/OBJECTIVES

The primary study aim is to assess the feasibility and acceptability of a randomised controlled trial of a remotely delivered program of Baduanjin mind-body exercise with participants diagnosed with any type and stage of cancer and receiving or who have received chemotherapy, and who have identified as having CRF. Remote delivery refers to providing the program over the internet and using the video conferencing software Zoom.

The secondary objectives are to determine the effectiveness and safety of the remotely delivered Baduanjin mind-body exercise program for CRF, with consideration to the design of a larger scale clinical trial. The long-term goal is to contribute to the evidence base of interventions for CRF and improve the quality-of-life outcomes for people living with CRF.

4. PARTICIPATING SITES

The Baduanjin mind-body exercise program will be mainly conducted online. However, supportive sessions (face-to-face) are available for participants in need at Liverpool Hospital, South Western Sydney Local Health District (SWSLHD) and Western Sydney University (WSU) campus. Study protocols, including the eligibility screening, participant communication, data collection and Baduanjin mind-body exercise program intervention

have been designed to be delivered remotely online using Zoom conferencing technology.

5. STUDY DESIGN

5.1 Study Type

A pilot randomised controlled feasibility study.

5.2 Expected Study Duration

The study duration is 10 weeks for participants in both the intervention group and waitlist control group. Potential participant interest might fluctuate from week-to-week depending on advertising exposure and oncologist referrals. Therefore, recruitment into the study will be staggered as people make their interest known to the research team and when they clear the study inclusion criteria. The trial period is from the date of ethics approval until December 2024 .

5.3 Data Source and Population

Participant's meeting study eligibility criteria will have their information collected using a study-specific Case Report Form. The form categories include demographic information (such as age, gender, ethnicity, language spoken at home), living arrangements, education and occupational status, and cancer type and treatment. (Refer to the Case Report Form).

The population are people diagnosed with any type and stage of cancer and receiving or who have received chemotherapy prior to study recruitment, and who have identified as having CRF.

To our knowledge, this will be the first study evaluating the feasibility and effects of Baduanjin mind-body exercise on cancer-related fatigue using a remote delivery method. Group sizes of 12 [26] and 15-20 per group are reported to give reasonable bias-corrected estimation of medium effect sizes in repeat-measure designed studies, as is being proposed for the current pilot [27]. For this pilot study, a sample size of $n = 29$ is necessary to have a 95% confidence of detecting an event which has a true probability of $\pi = 0.10$. To overcome the probable potential 15% participant attrition rate during the study [27] and to ensure availability of sufficient participants, a sample size of $n=40$ participants will be recruited in this study. Therefore, there will be 20 participants in the Baduanjin exercise, and another 20 participants in the control group. This number is sufficient to maximise

chances of identifying problems or feasibility issues that might arise with the intervention in preparation for a larger study [27].

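### The 95% chance of seeing a 10% problem holds for problems common to both arms; for problems only the 20 intervention participants can show, it is about 88%

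*Protocol*

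**What the plan says.** The sample size paragraph in section 1 (Summary, analysis considerations) states that "a sample size of n = 29 is necessary to have a 95% confidence of detecting an event" whose true probability is 0.10. It arrives at 40 by citing two things: randomisation into two groups at 1:1, and a possible 15% attrition, with a wish to have enough participants.

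Section 5.3 repeats the 29, the 0.10 and the 15%, arrives at 40, and concludes that "there will be 20 participants in the Baduanjin exercise, and another 20 participants in the control group". It closes by saying that this number is enough to maximise the "chances of identifying problems or feasibility issues that might arise with the intervention in preparation for a larger study". Just before the calculation, section 5.3 also cites group sizes of 12 and of 15 to 20 per group as adequate for estimating medium effect sizes.

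On exposure, section 5.8 says that waitlist participants do no Baduanjin from week 0 to week 9. They may join the program afterwards only outside the study, with no further questionnaires. Appendix 1 marks the Baduanjin Zoom sessions and the adverse event assessment for the intervention group only.

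**The concern.** The rule behind the 29 counts people in whom the event can occur and be observed. The protocol applies it to the total of two arms, then ends the paragraph by speaking of problems that arise with the intervention. Half of the total never meets the intervention during the study, so for that class of problem the relevant number is 20, which is below 29.

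The Summary adds to the difficulty by presenting 40 as allowing for the 1:1 split. The step from 29 to 40 is large enough for attrition but not for halving the sample.

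Feasibility is the primary aim, and the results are meant to inform a larger trial. A planner who sees no exercise-related adverse event of some kind, or no fault of some kind in the Zoom sessions, should know how likely it was that a 10% problem would go unseen. On the sample size text as it stands, that planner could take the chance to be 5%. It is about 12%, or up to about 17% with attrition.

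**Working it through.** **Inputs.** Assurance 95%, true event probability 0.10, stated requirement 29, total 40, 20 per arm, attrition 15% (sections 1 and 5.3). Exposure in the control arm during the study: none (section 5.8).

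**Formula.** With n independent participants who can each show the problem with probability p, the probability of seeing it at least once is 1 − (1 − p)^n.

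**Step 1: reproduce the 29.** The smallest n with 1 − 0.9^n ≥ 0.95 is ln(0.05)/ln(0.90) = 28.43, rounded up to 29. Check: n = 28 gives 0.9477 and n = 29 gives 0.9529. The stated figure is right.

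**Step 2: what the move from 29 to 40 covers.** Attrition alone needs 29/0.85 = 34.1, rounded up to 35. A total of 40 therefore covers attrition with five to spare. It does not cover the split: 95% within the intervention arm would need 29 evaluable exposed people, that is 35 allocated to that arm and 70 in total at 1:1.

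**Step 3: probability of seeing a 10% problem at least once.**

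| Who can show the problem | n | 1 − 0.9^n | Chance of missing it |
|---|---|---|---|
| Any participant, no attrition | 40 | 98.5% | 1.5% |
| Any participant, 15% attrition | 40 × 0.85 = 34 | 97.2% | 2.8% |
| Intervention arm, no attrition | 20 | 87.8% | 12.2% |
| Intervention arm, 15% attrition, leavers contribute nothing | 20 × 0.85 = 17 | 83.3% | 16.7% |

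**Step 4: the rate to which 95% does apply in the intervention arm.** Solving 1 − (1 − p)^n = 0.95 gives p = 1 − 0.05^(1/n). For n = 20, p = 0.139; for n = 17, p = 0.162.

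**The case against.** The best defence is that the protocol never attaches 95% to intervention problems in so many words. The 95% sentence speaks of an event without saying which kind. The sentence about the intervention comes later, carries no percentage, and is absent from the Summary. Read as covering any problem in the trial, the 95% is true and is exceeded. Most of the feasibility outcomes in section 10 (recruitment, conversion to enrolment, retention) do rest on the whole sample or a wider pool. This stands, and it limits the point to the scope of the claim. A reader might infer that the protocol promises 95% for intervention problems, or that 29 is miscalculated; the text supports neither. What remains is that one paragraph runs from the 29 to a conclusion about intervention problems without saying that the number exposed is 20, and that the Summary says the 1:1 allocation has been allowed for.

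Three further inferences also go too far:

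- **That the 29 is the sole numerical basis for the sample size.** Section 5.3 also cites 12 and 15 to 20 per group. Twenty per arm meets this, and 17 after attrition still lies within 15 to 20. Those figures concern estimation of effect sizes, so they do not repair the detection claim, but they are a second basis.
- **That 83% is the actual assurance.** Problems are picked up as they occur, through weekly calls, logbooks and daily contact with instructors. Someone who has a problem and then leaves has still shown it. With 15% attrition in the arm, the figure lies between 83% and 88%.
- **That adherence suffers the same shortfall.** Section 10 defines adherence as a proportion of those allocated to the intervention. It is estimated, not detected by a first occurrence, so this rule does not govern it.

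Nor does the protocol set a rule under which zero events would be read as excluding a 10% rate. The risk is one of interpretation and is not built into a decision.

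**Conclusion.** The point holds as a matter of scope. For problems that any participant can have, the 95% at a 10% rate is met with room to spare (98.5%, or 97.2% after attrition). For problems that only intervention participants can show, such as exercise-related adverse events and Zoom delivery problems, it is not met: 87.8% with all 20 observed, with a lower bound of 83.3%.

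The calculation assumes independent participants with a common 10% probability. The lower bound further assumes that 15% attrition falls equally on the two arms and that leavers contribute no information; heavier loss in the intervention arm would lower it. Even with no attrition the figure is 88%.

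Severity is moderate: a stated assurance needs correcting. A reader might conclude that 40 is too few and that the trial must grow to 70. The documents do not support that, since they nowhere require 95% within the intervention arm, and a somewhat lower assurance for one class of problem can be acceptable in a pilot if it is stated.

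**What to change.** Keep 40 participants and correct the sample size text in sections 1 and 5.3. Wording along these lines would do:

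> With 40 participants (34 after 15% attrition), the probability of observing at least once a problem with a true frequency of 10% exceeds 95% for problems that can occur in either arm. For problems specific to the intervention, to which 20 participants are exposed, this probability is about 88% (at least 83% allowing for 15% attrition in that arm). For these, 95% confidence applies to true frequencies of about 14% or more, or up to about 16% if those who leave contribute no information.

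In the Summary, also remove the suggestion that the step from 29 to 40 allows for the 1:1 split. The per-group sizes cited in section 5.3 for effect-size estimation can stay as they are.

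The cost is a few sentences in two places and a less favourable stated figure for one class of problem. Enrolment, outcomes, procedures and analysis do not change.

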5.4 Recruitment and Screening

Interested participants will be referred by their treating oncologist at Cancer Therapy Centre, Liverpool Hospital, other health practitioners or self-referral after seeing advertising for the study.

Resources required for the recruitment phase of the study include advertising materials (flyers and online advertisement). Only HREC approved participant recruitment material will be used during this study.

Advertising information will be placed on the noticeboards at Liverpool Hospital (SWSLHD) and the Western Sydney University campus. Online advertisement might be placed at the Wellness Centre, Liverpool Hospital and Western Sydney University website and via its Facebook and other social media pages to raise awareness of the study.

Potentially eligible study participants are screened from all people who have expressed an interest, and who have contacted a member of the research team or have given permission to their oncologist to be contacted by a member of the research team. The research team member will contact interested people over the phone to check their eligibility with the study inclusion/exclusion criteria using the Screening Checklist Form. Potentially eligible participants will then complete one question on a Brief Fatigue Inventory (BFI) score (simple fatigue scale) rating their CRF on a scale of 0 to 10 (0 = no fatigue; 10 = worst fatigue imaginable). If the screening process determines that fatigue is at a moderate level (4-6), they are eligible for study enrolment.

Participants who meet the inclusion criteria will be randomly assigned in a 1:1 ratio to the Baduanjin mind-body exercise group or the control group respectively.

[figure not shown]

Figure 1: Recruitment and screening flow chart

5.5 Inclusion Criteria

The inclusion criteria are: (1) 18 years of age or older; (2) receiving adjuvant chemotherapy or completed adjuvant chemotherapy; (3) medical history of cancer diagnosis; (4) suffering from moderate CRF (rating of 4 to 6) as assessed by the BFI simple fatigue scale; (5) have a computer / device that is Wi-Fi or hotspot connected and be able to use smart phones, email, phone camera, (such as Facetime on iPhone), and Zoom conferencing app; (6) be aware of one’s cancer diagnosis; and (7) understand the intervention process and able to communicate and provide informed consent in English.

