5.9 Randomisation

The participant will be randomised after they have met the inclusion criteria and completed the initial round of outcome measures (that is, baseline enrolment). At this time the participant will be randomised to 'Baduanjin mind-body exercise group' or 'waiting list control group' and receive a computer-generated 'Randomisation Number' based on a randomisation service software, the allocation concealment is undertaken by an independent research assistant.

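### People on adjuvant chemotherapy and people who finished it at any time are mixed, with no stratification factor named and feasibility rates pooled, so one treatment-timing factor should enter allocation, model and reporting

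*Protocol*

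**What the plan says.** **Who is eligible.** Section 5.5, criterion 2, admits people "receiving adjuvant chemotherapy or completed adjuvant chemotherapy". Section 5.3 describes the population as people with "any type and stage of cancer and receiving or who have received chemotherapy prior to study recruitment". Neither sets a window since the last treatment. The title in section 1 is narrower: "cancer-related fatigue in cancer participants receiving adjuvant chemotherapy".

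**How they are allocated.** Sections 1 and 5.4 give a 1:1 ratio and section 5.3 gives 20 per group. Section 5.9 says the allocation is "based on a randomisation service software, the allocation concealment is undertaken by an independent research assistant". It names no stratification factor, blocking or minimisation.

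**What is known about timing.** Section 2 states: "While most severe in the first 6 months following a cancer diagnosis or treatment, CRF can persist for years". It also reports that exercise and psychological treatments outperformed drugs "both during cancer treatment and in the cancer post-treatment stages", and cites two positive Baduanjin studies, in "colorectal cancer participants undergoing chemotherapy and breast cancer survivors who completed chemotherapy".

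**How results are reported.** Under section 10, recruitment, retention and adherence each have one denominator: enquiries, people potentially eligible, all enrolled, or the whole intervention group. The data analysis text allows demographic covariates where appropriate and says confounders will be explored. Treatment phase is not named, although section 5.3 records cancer type and treatment on the Case Report Form. The fatigue data are to supply an effect size for powering a larger trial.

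**The concern.** A person in the middle of chemotherapy and a person years past it may differ in how fatigue moves over the study weeks and in how well they cope with two sessions a day, six days a week. If so, two things follow.

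- With 20 per arm, the arms can differ by chance in their share of people on treatment, which would move the one BFI estimate that is meant to inform the next trial's power.
- A single adherence or retention rate does not show whether it applies to people on chemotherapy, the only group the title names.

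Stratified allocation has to be set before the first participant is randomised. A later analysis plan can add a covariate but cannot restore it.

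**Working it through.** **The plan's own figure.** Section 5.3 needs n = 29 for 95% confidence of seeing an event with probability 0.10. ln(0.05)/ln(0.90) = 28.43, rounded up to 29, and 1 − 0.90^29 = 0.953. This reproduces. With 15% attrition, 40 × 0.85 = 34, which is at least 29. Stratifying changes none of this.

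**Inputs.** From the protocol: N = 40, 20 per arm. Assumed, because the protocol gives no figure: 20-70% of participants on chemotherapy; a between-phase outcome difference d of 0.25 to 1.0 within-phase SD; exactly 20:20 allocation; no dropout; an analysis without treatment phase.

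**Chance of imbalance.** Let K of the 40 be on treatment and X of them fall in one arm. X is hypergeometric (40, K, 20), and the arms' shares differ by |2X − K|/20.

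| K (share) | P(≥ 20 points) | P(≥ 30 points) | SD of the difference in shares |
|---|---|---|---|
| 8 (20%) | 0.235 | 0.044 | 0.128 |
| 12 (30%) | 0.301 | 0.082 | 0.147 |
| 20 (50%) | 0.343 | 0.113 | 0.160 |
| 28 (70%) | 0.301 | 0.082 | 0.147 |

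These figures apply to any two-level factor with the same shares, including a split by time since treatment.

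**Shift given an imbalance.** Shift = imbalance × d. The standard error of the arm difference is √(2/20) = 0.316 SD.

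| d | 20 points: shift (in SE) | 30 points: shift (in SE) |
|---|---|---|
| 0.25 SD | 0.05 SD (0.16) | 0.075 SD (0.24) |
| 0.5 SD | 0.10 SD (0.32) | 0.15 SD (0.47) |
| 1.0 SD | 0.20 SD (0.63) | 0.30 SD (0.95) |

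In BFI points, if the natural change differed by 1 to 2 points between phases (again an assumption), the shift would be 0.2 × 1 to 0.2 × 2 = 0.2 to 0.4 at 20 points of imbalance, and 0.3 to 0.6 at 30.

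**Type I error and precision.** Simulation with no treatment effect (40,000 runs per setting, two-sample t-test at 5%, K = 12 and 20, d = 0.5 and 1.0):

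- Over all randomisations, the mean estimate is 0 to within simulation error and type I error is 0.049-0.050.
- Among randomisations with at least 30 points of imbalance, type I error is about 0.07 (d = 0.5) and 0.12-0.13 (d = 1.0).
- The variance of the unadjusted estimate exceeds the within-phase value of 0.1 by 5-7% (d = 0.5) and 22-25% (d = 1.0). The algebra agrees: for K = 20 and d = 1.0, 0.160² × 1.0²/0.1 = 0.256.

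**Feasibility precision (illustrative Wilson 95% intervals).** 16 of 20 adherent in the intervention arm gives 58-92%. 8 of 10 in one phase gives 49-94%.

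**The case against.** **Readings that go too far.** A reader might infer that the protocol itself says fatigue follows a different course on and after chemotherapy. It does not. Section 2 gives a severity gradient by time since diagnosis or treatment and says nothing about change over 8 weeks in either group. The two supporting studies differ in cancer type as well as phase, so they do not isolate phase. A reader might also infer that unstratified allocation biases the comparison. It does not: bias is zero on average and type I error is 5%. Nor is a sizeable imbalance more likely than not.

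**The case for leaving the plan alone.** A broad population is a legitimate choice for a feasibility pilot, and section 2 reports benefit in both phases. Entry requires a screening fatigue rating of 4 to 6, which narrows differences in starting severity. BFI change is listed as a secondary outcome. Treatment is recorded, covariates are allowed, and naming a covariate or tabulating by subgroup may properly sit in an analysis plan that is not shown. Even a 30-point imbalance with a 0.5 SD difference moves the estimate by less than half a standard error. Counts by phase would be imprecise.

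**What stands.** Most of this stands, and it makes the point modest. Four things remain:

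- The entry range limits starting level, not subsequent change.
- The Endpoints text in section 10 also places BFI change within the primary outcome measure endpoint.
- The named covariates are demographic, and confounders explored after the fact in 40 people are no substitute for a factor named in advance.
- Stratification cannot be added later.

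A plain receiving-versus-completed split also has a weakness: it puts someone who finished last week with someone who finished years ago, so it does not follow the gradient in section 2.

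**Conclusion.** The point holds in a limited form. The protocol mixes treatment phases with no time window, names no stratification factor, pools its feasibility rates and carries a title narrower than its entry criterion. Its own account of fatigue makes treatment timing plausibly prognostic.

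The comparison remains valid on average. What is at stake is precision, and the one realised estimate if chance imbalance occurs: 24-34% for 20 points or more and 4-11% for 30 points or more, over on-treatment shares of 20-70%. A 30-point imbalance would move the effect by 0.075 to 0.30 SD if the phases differ by 0.25 to 1.0 SD. The protocol supports neither the shares nor the differences with a figure, so these are ranges under assumption.

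For feasibility, it is unknown how many participants will be on chemotherapy. The pooled rates as defined would not show whether the result covers them. This is a worthwhile improvement and does not threaten the trial's validity.

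**What to change.** 1. **Section 5.9:** stratify the computer-generated list, in blocks, by one treatment-timing factor known at screening. On chemotherapy or within 6 months of completing it, versus later, matches the gradient in section 2. Receiving versus completed is simpler but follows that gradient less well.
2. **Section 10, data analysis:** include that factor and baseline BFI in the fatigue model.
3. **Section 10, feasibility:** report enrolment, retention and adherence counts for receiving versus completed chemotherapy as descriptive results, beside the overall rates.
4. **Section 5.3:** make sure time since last chemotherapy is recorded. The Case Report Form is not shown and may already hold it.
5. **Section 1:** reconcile the title with criterion 2.

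**Cost:** a setting in the randomisation software, one more screening item if it is not already collected, and one or two model terms. Arm sizes may differ by one or two, and rates by phase will have wide intervals. The sample size stays 40.
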